### 9.2.3. Adverse Events of Special Interest

Incyte defines AESIs and ECIs as a subset of TEAEs that investigators must rapidly communicate to Incyte for further evaluation. The AESI categories and the search strategy of each AESI are provided in Table 6. A separate SMQ file that includes all search strategies will be provided separately. The number and percentage of participants who have any AESI will be summarized.

**Table 6: Search Strategies for Adverse Events of Special Interest**

Adverse Event of Special Interest Category	Search Strategy
Serious infections	Serious AEs under SOC "Infections and Infestations"
Opportunistic infections	SMQ narrow "Opportunistic Infections"
Herpes zoster	Custom PT search strategy based on the HLT "Herpes viral infections" (refer to SMQ file)
Tuberculosis	HLT "Tuberculosis infections"
Malignancy (all types)	SMQ narrow "Malignant Tumors"
Cardiovascular events (eg, MACE)	MACE custom PT search (refer to SMQ file)
Other embolic and thrombotic events (eg, pulmonary embolism, deep vein thrombosis, thrombosis, cerebrovascular events)	SMQ "Embolic and thrombotic events"

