4. STUDY DESIGN

4.1. Overall Design

This is a Phase 2, double-blind, placebo-controlled, multicenter study of povorcitinib in participants with CSU on stable SOC with second-generation H1 antihistamines. The study will enroll approximately 136 participants in a 1:1:1:1 randomization ratio, stratified at baseline by previous anti-IgE biologic use (yes or no), into 1 of 4 treatment groups during the PC period (12 weeks) as shown in [Figure 1](#).

Treatment with study drug will start on Day 1 (baseline). After completing the 12-week PC period, participants will enter the 24-week EXT period. During the EXT period, the participants initially randomized to povorcitinib 15, 45, or 75 mg QD will continue taking povorcitinib at the same dose regimen. The participants initially randomized to placebo will be assigned to take 1 of these 3 dose regimens (ie, povorcitinib 15, 45, or 75 mg QD). Participants, investigators, and the sponsor will remain blinded to each participant's treatment assignment during the PC period. Participants and investigators will continue to remain blinded during the EXT period and post-treatment follow-up period.

Participants will receive study drug until completion of the 36-week treatment period or until 1 of the criteria for study treatment discontinuation are met. Participants will return for a follow-up visit approximately 60 days after their last dose of study drug.

All participants are required to maintain a stable dose of second-generation H1 antihistamine (SOC) during the study from the time of informed consent until the completion of the post-treatment follow-up visit. The SOC will be determined by the investigator. Further doses of second-generation H1 antihistamines may be used as rescue medication to treat worsening CSU symptoms at any time during the study. A 1-time, short course (maximum duration of 7 days) of glucocorticosteroids may be used as rescue medication after Week 4 in the case of severe exacerbation (see [Section 6.7.3](#)).

Efficacy will be evaluated using PROs, including the UAS7. Additional PRO outcomes are outlined in the SoA (see [Table 3](#)).

Safety and tolerability will be monitored throughout the study. The study will utilize an internal DSMB to monitor safety in addition to a CAC to adjudicate potential cardiovascular and thromboembolic AEs.

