5.7. Cardiovascular Adjudication Committee

An independent committee of physician experts in cardiovascular adjudication will be utilized to assess potential cardiovascular and thromboembolic AEs. Details will be described in a separate CAC charter.

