9.6.1. Adverse Events of Special Interest

Incyte defines AESIs as a subset of ECIs that an investigator must rapidly communicate to Incyte for further evaluation.

If an AESI meets the SAE definition (see Section 9.2), it must be reported following the requirements for an SAE indicated in Section 9.4.

The AESIs are as follows:

- Serious infections
 - Defined as any infection meeting SAE criteria (see Section 9.2)
- Opportunistic infections
- Herpes zoster
- TB
- Malignancy (all types)
- MACE, defined as any of the following:
 - Nonfatal MI
 - Nonfatal stroke of any classification, including reversible focal neurologic defects with imaging evidence of a new cerebral lesion consistent with ischemia or hemorrhage
 - Cardiovascular death defined as any of the following:
 - Death due to acute MI
 - Sudden cardiac death
 - Death due to heart failure
 - Death due to stroke
 - Death due to cardiovascular procedures
 - Death due to cardiovascular hemorrhage
 - Death due to other cardiovascular causes: peripheral artery disease
- Other embolic and thrombotic events (eg, pulmonary embolism, deep vein thrombosis, other thrombosis)

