10.4.3. Safety Analyses

Safety analyses will be conducted for the safety population. Adverse events will be coded by the MedDRA dictionary, and TEAEs (ie, AEs reported for the first time or worsening of a pre-existing event after first dose of study drug and until 60 days after the last dose of study drug) will be tabulated by preferred term and system organ class for all events, related events, and events of Grade 3 or higher. The Protocol-defined ECIs and AESIs will be tabulated by preferred term and Protocol-defined categories for all events. Quantitative safety variables (eg, laboratory values, vital signs) and their changes from baseline will be summarized with descriptive statistics. Clinically notable abnormal values will be flagged and tabulated based on predefined criteria.

The subset of AEs considered by the investigator to have a relationship to study drug will be considered to be treatment-related AEs. If the investigator does not specify the relationship of the AE to study drug, then the AE will be considered treatment-related. The incidence of AEs and treatment-related AEs will be tabulated.

The clinical laboratory data will be analyzed using summary statistics; no formal treatment group comparisons are planned. In addition, distributions of key laboratory parameters may be plotted over time; these values will also be classified into CTCAE v5.0 toxicity grades and tabulated. Descriptive statistics and mean change from baseline will be determined for vital signs at each assessment time. Vital sign results will be reviewed for clinically notable abnormalities. Descriptive statistics and mean change from baseline will be determined for each ECG parameter at each assessment time.

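### The SAP counts MACE and thromboembolic AESIs by term search only, gives the adjudication committee's decisions no place in the outputs, and alters the protocol's categories so that one stroke can sit in two rows

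*SAP*

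**What the plan says.** **Adjudication.** Protocol 5.7 states: "An independent committee of physician experts in cardiovascular adjudication will be utilized to assess potential cardiovascular and thromboembolic AEs". Protocol 4.1 describes the same body as "a CAC to adjudicate potential cardiovascular and thromboembolic AEs". Protocol Table 4 lists the committee among the mitigations for thromboembolic risk.

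**Definition.** Protocol 9.6.1 gives MACE three components:
- nonfatal MI;
- stroke, worded as "Nonfatal stroke of any classification, including reversible focal neurologic defects with imaging evidence of a new cerebral lesion consistent with ischemia or hemorrhage";
- death, introduced by "Cardiovascular death defined as any of the following" and followed by seven causes.

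A separate AESI category is "Other embolic and thrombotic events (eg, pulmonary embolism, deep vein thrombosis, other thrombosis".

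**Tabulation rule.** Protocol 10.4.3 says: "The Protocol-defined ECIs and AESIs will be tabulated by preferred term and Protocol-defined categories for all events".

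**SAP.** In SAP 9.2.3, Table 6 replaces the MACE category with a broader cardiovascular one in which MACE is only an example. Its search strategy is "MACE custom PT search (refer to SMQ file". The neighbouring category reads "Other embolic and thrombotic events (eg, pulmonary embolism, deep vein thrombosis, thrombosis, cerebrovascular events" and is filled by a standardized MedDRA query. SAP 9.2.3 says the search strategies are held in a separate file, which is not part of the documents. The visible SAP text mentions neither the CAC nor adjudication, and Appendix A lists no output of adjudicated events. SAP 11.1, on changes to protocol-defined analyses, declares nothing on this point.

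**The concern.** The trial plans expert decisions on whether a suspected cardiovascular or thromboembolic event is real and how to classify it. The analysis plan then reports these events from coded terms alone. An event the committee rejects can stay in the row, and one it confirms can be missing from it if the investigator's term falls outside the search list. A reader of the study report could not tell which had happened.

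The categories have also shifted. Stroke is a MACE component in the protocol, yet the SAP names cerebrovascular events in the row meant for other thrombotic events. The table shows no rule for an event that fits both.

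The stake is how a small number of safety events are read. Protocol Table 4 names MACE and thrombosis among the risks seen with other JAK inhibitors and reports pulmonary embolism in 2 povorcitinib participants, who had multiple independent risk factors.

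**Working it through.** The plan gives no figure to reproduce. The check is a comparison of texts, followed by simple arithmetic on scale.

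**Step 1: what a coded term can supply for each MACE component in Protocol 9.6.1.**

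| Component | From a preferred term (with fatal outcome where relevant) | Left unsettled |
|---|---|---|
| Nonfatal MI | Yes, if coded as MI | Whether the CAC agrees |
| Overt nonfatal stroke | Yes, if coded as stroke | Whether the CAC agrees |
| Reversible focal deficit | The deficit only | Whether imaging shows a new lesion |
| Cardiovascular death, seven causes | Some causes, if coded as such | Attribution when the term does not state the cause |

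The search therefore covers part of the definition and leaves two elements open.

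**Step 2: does the SAP use a defining criterion elsewhere?** Yes. In SAP 9.2.4, the creatinine, transaminase and CPK events are analysed mainly on the laboratory threshold that defines them, with a term search as a supplement. For MACE, the term search stands alone.

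**Step 3: can one stroke fall in two rows?** The SAP's label places cerebrovascular events in the other embolic and thrombotic row. There are three possibilities for the unseen MACE term list:
- It includes stroke terms, as the protocol's definition requires, and there is no exclusion rule. The stroke then appears in both rows.
- It leaves stroke out. The MACE row then omits a protocol component.
- It includes stroke, and the file removes MACE events from the other row. The overlap is then resolved, but the SAP does not say so.

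MI may raise the same question, because Protocol Table 8 and 6.6.1.4 class both MI and stroke as arterial thrombosis.

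**Step 4: which outputs are affected?** The outputs affected are the category rows of Tables 3.2.17.x to 3.2.19.x in SAP Appendix A. The overall summary in SAP 9.2.3 counts participants with any AESI, so a participant with one stroke counts once there.

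**Step 5: scale.** Inputs are from Protocol 10.1: about 136 participants in 4 equal groups.
- Per group: 136 / 4 = 34.
- Randomized to povorcitinib: 3 × 34 = 102.
- One event in one group: 1 / 34 = 2.9%.
- One event among all randomized to povorcitinib: 1 / 102 = 1.0%.
- One stroke shown in both rows: 1/34 in each, so the two rows sum to 2 for 1 event.

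**The case against.** The strongest reply is that the SAP's method is largely the protocol's. Protocol 10.4.3 itself calls for tabulation by preferred term, and nothing in the protocol says the AESI tables must use CAC-confirmed events. Committee details are left to a charter that is not in the documents. This stands. Preferred-term tables are not a protocol violation, and adding adjudicated results is a better method, not a missed requirement. The protocol's categories, however, are required by the same sentence of 10.4.3, and Table 6 does not keep them.

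A reader might infer that the SAP cannot apply the MACE definition at all. The documents do not support that. MI and overt stroke can be found by term, and the imaging condition attaches only to reversible deficits. Fatal events are tabulated and listed (Listing 2.7.4), and AESIs have a listing (2.7.8), so individual cases can be inspected. Those listings are not described as carrying the CAC's decision.

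A reader might also infer that the AESI total is inflated. It is not, because the overall summary counts participants. Nor are AESI categories exclusive in general: a serious tuberculosis infection fits two rows of the protocol's own list. For thrombosis, though, both documents use the word other, which signals separation from MACE. The term lists are unseen and may contain an exclusion, but the SAP describes the file as holding search strategies, not adjudication results.

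Finally, 1/34 is the size of any single event in a group. It is not a demonstrated error, and the documents do not show how often the committee and the search would disagree. Nor are MACE and thrombosis singled out as the leading class risks: Protocol Table 4 also lists serious infections and malignancies as observed with other JAK inhibitors.

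**Conclusion.** The point holds as a gap in reporting and a departure from the protocol's categories. SAP 9.2.3 gives the adjudication no visible route into the results. Imaging for reversible deficits and the attribution of some cardiovascular deaths therefore stay unsettled in the MACE row, and the rows can differ from the committee's decisions. The relabelled categories allow one stroke to appear in two rows.

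The effect is limited to how a few safety events are classified. Any single event moves a group's row by 2.9 percentage points, or the povorcitinib total by 1.0. Efficacy conclusions and the any-AESI participant count are not affected.

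This rests on three assumptions: the search file holds no adjudication data or exclusion rule, as the SAP's description of it suggests; redacted SAP text does not cover the point; and few such events occur in a trial of this size. It is a worthwhile, inexpensive improvement, not a flaw that threatens the trial's conclusions.

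**What to change.** In SAP 9.2.3 and Appendix A:
- Add a table or listing of CAC-adjudicated events, showing MACE by protocol component and thromboembolic events separately, with the committee's decision for each suspected event, including those rejected or left undecided.
- Keep the preferred-term and standardized-query tables as supportive outputs and as the means of finding candidates.
- Restore the category labels of Protocol 9.6.1, or declare the change and its reason in SAP 11.1.
- State that events confirmed as MACE are excluded from the other embolic and thrombotic row.

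The cost is SAP wording, some programming and a merge of adjudication outcomes the trial already plans to produce. No new assessment of participants is needed. The documents do not describe how CAC outcomes are stored, so the effort of the merge should be confirmed against the charter.

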### 9.2.4. Events of Clinical Interest

An ECI is an AE that Incyte wishes to document in an organized manner for monitoring or understanding. The ECI categories and the search strategy of each ECI are provided in Table 7.

**Table 7: Search Strategies for Events of Clinical Interest**

Event of Clinical Interest Category	Search Strategy
Increased serum creatinine ( $> 3 \times$ ULN or $> 3 \times$ baseline) and renal dysfunction	
 
Laboratory parameter: Identify all participants with outlier laboratory test values
 
PT assessment: custom SMQ based on SMQ broad "Acute renal failure" (refer to SMQ file)
 

Hepatic events and increased hepatic transaminases ( $> 5 \times$ ULN)	
 
Laboratory parameter: Identify all participants with outlier laboratory test values
 
PT assessment: SMQ narrow "Drug-related hepatic disorders" comprehensive search
 

Increased CPK ( $> 5 \times$ ULN)	
 
Laboratory parameter: Identify all participants with outlier laboratory test values
 
PT assessment: custom SMQ based on SMQ narrow "Rhabdomyolysis/myopathy" (refer to SMQ file)
 

Acne	Custom PT search (refer to SMQ file)

The ECIs of increased serum creatinine, increased hepatic transaminases, and increased CPK will be predominantly laboratory parameter-based analyses assessing outlier participants. The number and percentage of participants who have increased serum creatinine, ALT, AST, or CPK will be summarized or listed.

In addition, a separate PT search will supplement the laboratory-based analysis. The number and percentage of participants who have any relevant PTs will be summarized or listed.

### **9.3. Clinical Laboratory Tests**

#### **9.3.1. Laboratory Value Definitions**

Laboratory values, change from baseline values, and percent change from baseline values will be summarized descriptively by visit, and non-numeric test values will be tabulated when necessary. Baseline will be determined according to Section 4.1.3. The last record before administration in the highest priority will be considered the baseline record. For baseline laboratory candidates with the same date and time in the same priority category, additional rules may be provided after consultation with the medical monitor to delineate which value will be defined as baseline.

#### **9.3.2. Laboratory Value Summaries**

All test results and associated normal ranges from central laboratories will be reported in SI units. All tests with numeric values will have a unique unit per test. Any laboratory test results and associated normal ranges from local laboratories will be converted to SI units.

When there are multiple nonmissing laboratory values for a participant's particular test at a scheduled visit, central laboratory values have higher priority over local laboratory values. If a tie still exists, the laboratory value with the smallest laboratory sequence number will be used in by-visit summaries. In addition, box plots will be provided for creatine kinase, hemoglobin, hematocrit, platelet count, high-sensitivity C-reactive protein, IgE, lymphocyte absolute count, neutrophil absolute count, white blood cell count, basophil cell count, eosinophil cell count, total cholesterol, HDL, LDL, HDL/LDL ratio, ALT, and AST.

For test results that will be summarized with available normal ranges, the number and percentage of participants with laboratory values that are low (but never high), normal, high (but never low), and both low and high will be calculated for each test. This shift summary will be produced for each test. The denominator for the percentage calculation will use the number of participants in the baseline category (ie, low, high, normal, missing) as the denominator for the percentage in each of the categories during the study.

Severity grades will be assigned to laboratory test values based on the numerical component of CTCAE v5. Shift tables will also be presented showing change in CTCAE grade from baseline to the worst grade postbaseline. Separate summaries for abnormally high and abnormally low laboratory values will be provided when the laboratory parameter has both high and low grading criteria. The denominator for the percentage calculation will be the number of participants in the baseline category. The number of participants who experienced worsening of laboratory abnormalities will be summarized by maximum severity.

### 9.3.3. Potentially Clinically Important Laboratory Values

Criteria for potentially clinically important laboratory values are listed in [Table 8](#). The number and percentage of participants with postbaseline laboratory values that meet each criterion will be summarized at each scheduled visit by treatment group. Participants with potentially clinically important laboratory values will also be listed.

**Table 8: Criteria for Potentially Clinically Important Laboratory Values**

Laboratory Parameter	Grade (Criteria)
Hemoglobin	Grade 2 (80 to < 100 g/L) Grade 3 (< 80 g/L)
Lymphocytes	Grade 2 (0.5 to < 0.8 × 10  /L) Grade 3 (0.2 to < 0.5 × 10  /L) Grade 4 (< 0.2 × 10  /L)
Neutrophils	Grade 2 (1.0 to < 1.5 × 10  /L) Grade 3 (0.5 to < 1.0 × 10  /L) Grade 4 (< 0.5 × 10  /L)
Platelets	Grade 2 (50 to < 75 × 10  /L) Grade 3 (25 to < 50 × 10  /L) Grade 4 (< 25 × 10  /L)
Creatinine	Grade 2 (> 1.5 to 3 × ULN or > 1.5 to 3 × baseline) Grade 3 (> 3 to 6 × ULN or > 3 × baseline) Grade 4 (> 6 × ULN)
Creatine kinase	Grade 2 (> 2.5 to 5 × ULN) Grade 3 (> 5 to 10 × ULN) Grade 4 (> 10 × ULN)
ALT AST	Grade 3 (> 5 to 10 × ULN) Grade 3 (> 5 to 10 × ULN)
Estimated glomerular filtration rate	Grade 3 (15 to < 30 mL/min/1.73 m  )

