ALT and/or AST is $> 20.0 \times$ ULN	
Step 1: Discontinue study drug administration and have the participant follow EOT visit procedures; a post-treatment follow-up visit (EOS) is also recommended.
 
Step 2: In parallel to the participant starting the post-treatment follow-up period, the investigator, in collaboration with the medical monitor, will determine further steps.

CPK is $> 5.0 \times$ ULN	
Step 1: Evaluate if there are symptoms suggestive of myositis or rhabdomyolysis. Additionally, the investigator may repeat the test for confirmatory purposes.
 
Step 2: If there are no symptoms suggestive of myositis or rhabdomyolysis, the participant may continue study drug at the investigator's discretion. Appropriate monitoring should be conducted.
 
Step 3: If symptoms suggestive of myositis or rhabdomyolysis are identified, interrupt study drug and contact the medical monitor (or designee).

Table 8: Guidelines for Interruption, Restarting, and Discontinuation of Study Drug (Continued)

Laboratory Value	Action Taken
Hematology	
Platelet count is $< 50 \times 10^9/L$	
Step 1: Interrupt study drug administration.
 
Step 2: Repeat platelet count assessment promptly, within 7 days, to confirm value.
 
Step 3: Repeat platelet count assessment weekly until platelet count reaches $\geq 100 \times 10^9/L$ and then restart study drug at the same dose.
 
If platelet count does not increase to $\geq 100 \times 10^9/L$ after 3 weeks of drug interruption, study drug will be permanently discontinued, and the participant will follow EOT visit procedures; a post-treatment follow-up visit (EOS) is also recommended.

ANC is $< 1.0 \times 10^9/L$	
Step 1: Interrupt study drug administration until the toxicity has resolved to $\geq 1 \times 10^9/L$ or the baseline value.
 
Step 2: Restart study drug at the same dose and monitor as clinically indicated.

Hemoglobin is 8 to < 9 g/dL or > 2-g/dL decrease from baseline.
 
Note: If the decrease results in a value < 8 g/dL, then follow the guidance below.
	
Step 1: Interrupt study drug administration until the toxicity has resolved, with hemoglobin meeting the criteria of ≤ 2-g/dL decrease from baseline.
 
Step 2: Evaluate medical history to determine if the decrease in hemoglobin was likely related to underlying disease or investigational drug.
 
Step 3: Restart study drug and monitor as clinically indicated.

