3.3.2.3.1	Shift Summary of Lipid Panel Laboratory Values - to the Worst Abnormal Value	Safety	X
3.3.3.1.x	Shift Summary of Hematology Laboratory Values in CTCAE Grade - to the Worst Grade Abnormal Value	Safety/EXT-Evaluable	X
3.3.3.2.x	Shift Summary of Chemistry Laboratory Values in CTCAE Grade - to the Worst Grade Abnormal Value	Safety/EXT-Evaluable	X
3.3.3.3.1	Shift Summary of Lipid Panel Laboratory Values in CTCAE Grade - to the Worst Grade Abnormal Value	Safety	X

Table No.	Title	Population	Standard
3.3.4.x	Summary of Potentially Clinically Important Laboratory Values by Visit	Safety/EXT-Evaluable	X
3.3.5.x	Summary of Potential Drug-Induced Liver Injury Events by Visit	Safety/EXT-Evaluable,	
3.4.1.x	Summary of Systolic Blood Pressure During the PC Period	Safety/EXT-Evaluable	X
3.4.2.x	Summary of Diastolic Blood Pressure During the PC Period	Safety/EXT-Evaluable	X
3.4.3.x	Summary of Pulse During the PC Period	Safety/EXT-Evaluable	X
3.4.4.x	Summary of Respiratory Rate During the PC Period	Safety/EXT-Evaluable	X
3.4.5.x	Summary of Body Temperature During the PC Period	Safety/EXT-Evaluable	X
3.5.1.1.x	Summary of PR Interval (ms) From 12-Lead ECG by Visit During the PC Period	Safety/EXT-Evaluable	X
3.5.1.2.x	Summary of QRS Interval (ms) From 12-Lead ECG by Visit During the PC Period	Safety/EXT-Evaluable	X
3.5.1.3.x	Summary of QT Interval (ms) From 12-Lead ECG by Visit During the PC Period	Safety/EXT-Evaluable	X
3.5.1.4.x	Summary of QTcF Interval (ms) From 12-Lead ECG by Visit During the PC Period	Safety/EXT-Evaluable	X
3.5.1.5.x	Summary of Heart Rate (bpm) From 12-Lead ECG by Visit During the PC Period	Safety/EXT-Evaluable	X
3.5.1.6.x	Summary of Clinically Significant ECG Abnormality by Visit During the PC Period	Safety/EXT-Evaluable	X

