### Listings

Listing No.	Title
2.1.1	Participant Enrollment and Disposition Status
2.1.2	Participant Inclusion and Exclusion Criteria Violations
2.2	Protocol Deviations
2.3	Analysis Populations
2.4.1	Demographic and Baseline Characteristics
2.4.2	Disease History
2.4.3	Prior Therapy for Chronic Spontaneous Urticaria
2.4.4	Medical History
2.4.5	Prior and Concomitant Medications
2.5.1	Study Drug Exposure and Compliance
2.7.1	Adverse Events
2.7.2	Serious Adverse Events
2.7.3	Grade 3 and Higher Adverse Events
2.7.4	Fatal Adverse Events
2.7.5	Treatment-Related Adverse Events
2.7.6	Adverse Events Leading to Dose Interruption
2.7.7	Adverse Events Leading to Discontinuation of Study Drug
2.7.8	Adverse Events of Special Interest
2.7.9	Events of Clinical Interest
2.8.1.1	Clinical Laboratory Values - Hematology
2.8.1.2	Clinical Laboratory Values - Chemistry
2.8.1.3	Clinical Laboratory Values - Lipid Panel
2.8.2.1	Abnormal Clinical Laboratory Values - Hematology

Listing No.	Title
2.8.2.2	Abnormal Clinical Laboratory Values - Chemistry
2.8.2.3	Abnormal Clinical Laboratory Values - Lipid Panel
2.8.3	Potentially Clinically Important Laboratory Values During the PC Period
2.8.4	Potential Drug-Induced Liver Injury Events During the PC Period
2.9.1	Vital Signs
2.9.2	Abnormal Vital Sign Values
2.9.3	Alert Vital Sign Values
2.10.1	12-Lead ECG Values
2.10.2	Abnormal 12-Lead ECG Values
2.10.3	Alert 12-Lead ECG Values

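### SAP Table 8 stops at 10 × ULN for ALT and AST and at 15 for eGFR, so the most extreme values of these three parameters meet no criterion of their own

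*SAP*

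**What the plan says.** SAP Table 8 covers nine laboratory parameters. ALT and AST share an entry that reads "Grade 3 (> 5 to 10 × ULN) Grade 3 (> 5 to 10 × ULN", one band each with nothing above it. The eGFR entry is "Grade 3 (15 to < 30 mL/min/1.73 m"², with nothing below it. Creatine kinase, directly above ALT and AST, reads in its last two lines "Grade 3 (> 5 to 10 × ULN) Grade 4 (> 10 × ULN".

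SAP 9.3.3 puts these bands to use in two ways. Postbaseline "values that meet each criterion will be summarized at each scheduled visit by treatment group", and "Participants with potentially clinically important laboratory values will also be listed". In SAP Appendix A the outputs are Table 3.3.4.x, "Summary of Potentially Clinically Important Laboratory Values by Visit", and Listing 2.8.3, "Potentially Clinically Important Laboratory Values During the PC Period".

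**The concern.** A table meant to pick out worrying values should not let a value leave the count because it has become worse. With closed bands, an ALT or AST that passes 10 × ULN looks in Table 3.3.4.x like a case that has cleared. A participant whose only raised value is above 10 × ULN never appears in the ALT or AST row.

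The creatine kinase entry shows that Grade 3 in this table does not mean Grade 3 or higher: where Grade 4 is wanted, it is written out. The uncounted range also contains ALT or AST above 20 × ULN, where the protocol's own Table 8 (section 6.6.1) says "Step 1: Discontinue study drug administration and have the participant follow EOT visit procedures". That is cited only to show that the range matters to this trial.

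At stake is the consistency of two by-visit safety tables in the same report. The efficacy analyses are not involved.

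**Working it through.** The plan states no figure to reproduce. The check codes each band as an interval and classifies test values.

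**Inputs.** SAP Table 8: ALT and AST 5 < x ≤ 10 (× ULN); creatine kinase 2.5 < x ≤ 5, 5 < x ≤ 10 and x > 10 (× ULN); eGFR 15 ≤ x < 30; creatinine Grade 2 from above 1.5 to 3 × baseline and Grade 3 above 3 × baseline. SAP 9.3.4: ALT cut-offs at or above 3, 5, 10 and 20 × ULN. Protocol Table 6: exclusion for eGFR below 45.

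**Step 1: which parameters are open at the extreme?** Open: hemoglobin (< 80 g/L), lymphocytes (< 0.2 × 10⁹/L), neutrophils (< 0.5 × 10⁹/L), platelets (< 25 × 10⁹/L), creatinine (> 6 × ULN) and creatine kinase (> 10 × ULN), which is 6 of 9. Closed: ALT, AST and eGFR, which is 3 of 9.

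**Step 2: classify test values.**

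| Value (× ULN) | Table 8, ALT | Table 8, creatine kinase | DILI ALT rows met (of 4) |
|---|---|---|---|
| 8 | counted | Grade 3 | 2 |
| 12 | not counted | Grade 4 | 3 |
| 15 | not counted | Grade 4 | 3 |
| 25 | not counted | Grade 4 | 4 |

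For a participant at 8 and then 15 × ULN, the Table 8 ALT count goes from 1 to 0 while the DILI rows met go from 2 to 3. The same two values for creatine kinase give 1 and then 1. AST behaves as ALT does. For eGFR, 20 lies in the band and 10 does not, so a fall from 20 to 10 also takes the count from 1 to 0.

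**Step 3: do the creatinine rows cover eGFR below 15?** Assume eGFR varies as creatinine to the power −k, with k between 1.0 and 1.2. This is an assumption and does not come from the documents. A fall from 45 to 15 multiplies creatinine by (45/15)^(1/k) = 3^(1/k):

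- k = 1.0: 3.00
- k = 1.1: 2.71
- k = 1.2: 2.50

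All exceed 1.5, so a Grade 2 or Grade 3 creatinine row counts the participant. The smallest Day 1 eGFR for which a fall to 15 brings creatinine to 1.5 × baseline is 15 × 1.5^k:

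- k = 1.0: 22.5
- k = 1.1: 23.4
- k = 1.2: 24.4

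On the × baseline criterion, the cover therefore fails only if eGFR on Day 1 had already dropped to roughly half the entry limit (22.5/45 = 0.50; 24.4/45 = 0.54).

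**The case against.** The best case against the point is that little is lost.

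- **Other displays.** SAP 9.3.4 counts ALT and AST at or above 10 and 20 × ULN at each scheduled visit and lists the participants. Its Table 3.3.5.x follows straight after Table 3.3.4.x, for the same populations. The ECI rule above 5 × ULN has no upper limit (SAP 9.2.4), the worst-grade shift tables (SAP 9.3.2) include the top grades, and Appendix A also has chemistry listings. All of this stands, and it is why the point is minor. It does not make Table 8 right: two neighbouring tables would move in opposite directions for the same participant.
- **The 8-then-15 pattern should be uncommon.** Protocol Table 8 calls for interruption above 3 × ULN with weekly repeats, and scheduled visits are four weeks apart. This also stands. It does not touch the simpler case of one scheduled value above 10 × ULN, which meets no ALT or AST criterion at all.
- **The eGFR part is close to theoretical.** Step 3 supports this. Protocol Table 9 lists creatinine but not eGFR among the analytes. If eGFR is derived and reported as a test, the general shift tables might show it, although the SAP names no eGFR display other than the Table 8 band.
- **The final layout is not visible.** Appendix A marks Table 3.3.4.x as a standard table and supplies no study-specific shell for it. A standard program might already carry the missing categories, but the SAP's written criteria do not.

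**Conclusion.** The point holds as a minor error in a stated rule. Three of the nine parameters in SAP Table 8 have no open-ended worst category, and following SAP 9.3.3 literally gives a wrong count at the extreme for each of them. The transaminase signal is not lost from the report as a whole, and the creatinine rows should catch nearly every participant with an eGFR below 15, given k between 1.0 and 1.2. How many participants would be affected cannot be derived from the documents.

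The conclusion assumes that Table 8 is complete as it reads. A lost Grade 4 line for ALT, AST or eGFR cannot be ruled out entirely, but it is unlikely because the multi-grade entries for the other parameters are intact.

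**What to change.** In SAP Table 8, add three open-ended categories: ALT > 10 × ULN, AST > 10 × ULN and eGFR < 15 mL/min/1.73 m². Carry them into the code for Table 3.3.4.x and Listing 2.8.3.

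The cost is three lines in one SAP table and the matching programming. No new data are collected, and no clinical rule or efficacy analysis changes.
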